ATLAS A pragmatic randomised double-blind trial of Antipsychotic Treatment of very LAte-onset Schizophrenia-like psychosis

ATLAS

Statistical Analysis Plan

Version Number: 1.0

Prepared by: [name] and [name]

1. Introduction

This document gives a detailed statistical analysis plan for the ATLAS trial, and should be read in conjunction with the current protocol.

2. Background

Very late-onset schizophrenia-like psychosis is a common condition, which affects an estimated 34,000 of the UK population aged over 60 and with 2,800 new service contacts each year. After dementia and depression, these patients represent the largest diagnostic group presenting to Old Age Psychiatry services. Impairments in quality of life associated with psychosis are severe and comparable to those seen in younger schizophrenia patients and elderly people with dementia. Patients often suffer the effects of their delusional beliefs for 10 or 20 years and this has a negative impact upon their families, neighbours and local social and housing services.

Antipsychotic drugs are widely used to treat late-onset (i.e. age ≥ 60) schizophrenia-like psychosis patients but this practice is not evidence-based. A Cochrane review concludes that there is no reliable clinical trial evidence upon which to base treatment guidelines. Potential benefits of antipsychotic drugs cannot currently be quantified without proper clinical trial evaluation and need to be balanced against potential risks of such treatment. A large randomised trial is urgently needed to assess reliably the balance of benefits and risks of antipsychotic drugs in late-onset schizophrenia-like psychosis.

3. Trial objectives and design

ATLAS is a multi-centre randomised controlled trial with the following objectives:

Primary objectives

- 1) To determine whether 12 weeks' treatment with amisulpride is superior to placebo in reducing symptoms of very late-onset schizophrenia-like psychosis as measured by the Brief Psychiatric Rating Score (BPRS) and by numbers of patients withdrawn to open treatment by their physicians because of perceived lack of efficacy. A prior hypothesis is that benefits of amisulpride will be most apparent on hostility, suspiciousness, hallucinations, tension, uncooperativeness and motor hyperactivity sub-scores of the BPRS.
- 2) To determine whether any benefits of amisulpride are maintained by prolonging treatment beyond 12 weeks. Duration of stage 2 treatment was initially 24 weeks but was then reduced to 12 weeks, to enhance numbers still on treatment at their final assessment.

Secondary objectives

ATLAS will also investigate:

- (i) The associated risks of side-effects and serious adverse events;
- (ii) Compliance with allocated treatment;
- (iii) The effects of treatment on quality of life;
- (iv) The cost-effectiveness of amisulpride treatment.

Trial design

ATLAS is a pragmatic, randomised, 3-arm, double-blind placebo-controlled trial with two stages:

Stage 1 – an initial double-blind placebo-controlled stage to investigate efficacy and tolerability of oral amisulpride (arms A and B) versus placebo (arm C) over 12 weeks.

Stage 2 – a second double-blind stage investigating the effects of treatment continuation (arm A) versus switching to placebo (arm B) over a further 24 (initially, later 12) weeks.

Randomisation (3 Groups)

 Stage 1 – Weeks 1-12	 Stage 2 – Weeks 13-24 (or 36)	
(A) Amisulpride		Amisulpride
(B) Amisulpride		Placebo
(C) Placebo		Amisulpride

Outcome measures

Primary Efficacy Parameter – Brief Psychiatric Rating Scale

The first primary outcome measure is the Brief Psychiatric Rating Scale (BPRS), a widely used clinician-rated instrument for assessing positive, negative and affective symptoms in patients with psychotic disorders. The BPRS consists of 18 symptom constructs. Each item is assessed by the rater on a 7-point scale ranging from 1 (not present) to 7 (extremely severe). The total score is obtained by summing the scores from the 18 items. Scores thus range from 18 to 126, with higher scores indicating greater levels of psychopathy. The BPRS will be administered at baseline, at week 4, then again in weeks 10-12, week 16 and the final assessment (weeks 22-24 or 34-36). Change in BPRS score between baseline and the week 10-12 assessment and between the week 10-12 and final assessments are the trial's co-primary outcomes.

The second primary outcome measure is the proportion of patients withdrawn to open treatment by their physicians because of perceived lack of efficacy.

Secondary Efficacy Parameters

(i) Extrapyramidal side effects (EPSE) measured with the Simpson-Angus Scale (SAS). The modified SAS used in ATLAS measures nine extrapyramidal signs: gait, arm dropping, shoulder shaking, elbow rigidity, wrist rigidity, leg pendulousness, glabellar tap, tremor and salivation, all of which are assessed by direct examination. Each item is rated on a scale of 0-4, with higher scores indicating greater severity of EPSE. The scale range of the modified SAS is thus 0-36. The SAS has been widely used to measure EPSE within clinical trials and will be administered at baseline, then again at week 4, weeks 10-12, week 16 and weeks 22-24 (initially 34-36). The change in SAS between baseline and week 10-12 and between week 10-12 and the final assessment (week 22-24 or 34-36) will be compared between groups to assess EPSE.

(ii) **Compliance** expressed as treatment discontinuation rates and as percentage of prescribed trial medication taken between weeks 1 and 10-12 and between weeks 13 and the final assessment will be compared in patient allocated to receive amisulpride and those allocated placebo.

(iii) Quality of life measured with the self-rated, 26-item, WHO Quality of Life Scale (WHOQOL-BREF) at baseline, 10-12 weeks and the final assessment. The WHOQOL-BREF includes two items about an individual's overall perception of their quality of life and health and questions assessing four

domains; physical, psychological, social and environmental well-being, which higher scores denoting a better quality of life.

A separate analysis plan for the cost-effectiveness will be drafted.

Sample size considerations

Because of the likely problems with recruitment and retention of patients with late-onset, schizophrenia-like psychosis, ATLAS included an initial Feasibility Phase following which, a pragmatic decision was made to reduce the target sample size from 200-300 to at least 100 participants, to be recruited by mid-2016. The statistical power calculations have been amended with the main emphasis being to answer the primary stage 1 question of whether 12 weeks of amisulpride provides worthwhile benefit. The minimal clinically relevant difference (MRD), given the potential hazards of antipsychotic drugs, is considered to be 5 points on the BPRS. We estimate that the standard deviation of BPRS scores will be 9 points. We are thus powering the trial on a minimal worthwhile standardised effect size of 0.56 (=5/9) standard deviations, a moderate treatment effect.

With 100 patients, allowing for a 10% drop-out rate by 12-weeks, i.e. 90 of 100 with outcome assessments, ATLAS would have 70% power at 2p<0.05 to detect the MRD of 5 points between those taking amisulpride and placebo in stage 1, and ample power to detect larger differences.

4. General considerations

Study population:

Primary analyses of each stage will include all patients who have taken any study treatment in that stage. Participants who withdrew after pack allocation but before receiving any treatment can be safely excluded as treatment allocation is double-blinded so treatment allocation cannot influence the decision to withdraw and so introduce selection bias. Analyses of this population will be by intention to treat (ITT), ie all participants will be analysed in the treatment arm to which they were randomised, whether or not they adhered to the treatment. This is to avoid any potential bias in the analysis. Secondary analysis such as 'per protocol' (only those participants who adhere with the treatment allocation) may be carried out but as a sensitivity analysis only.

P-values:

Unless otherwise specified, estimates of amisulpride efficacy will be presented with 95% confidence intervals. P-values will be from two-sided test. No corrections for multiple testing will be made in the primary analyses.

Missing data:

The primary endpoint will be analysed using repeated measures analyses of all available data, which minimises impact of missing data. If a score is missing for a participant it is just missing. It has no effect on the other scores from the same participant.

Late data:

The week 4 and week 16 assessments should, where possible, be undertaken within ± 7 days of the scheduled date. The other assessments (e.g. 10-12 week and 22-24 week) allow a ± 14 day leeway. As deviations from scheduled assessments are possible in a study of participants with very late-onset schizophrenia-like psychosis assessments outside these windows will be included as if at the specified time point with no specified time limit.

Timing of interim analyses:

Interim analyses of efficacy and safety will be completed yearly as part of the Data Monitoring and Ethics Committee (DMEC) reviews of accruing data. No formal stopping rules based on interim analyses will be applied. The DMEC will inform the Trial Steering Committee (TSC) if, in their view, information from unblinded analyses of interim data provide proof beyond reasonable doubt that one of the treatments under investigation is either clearly indicated or contraindicated, either for all participants or for a particular subgroup of trial participants. Appropriate criteria of proof beyond reasonable doubt cannot be specified precisely, but a difference of at least three standard deviations in an interim analysis of the primary endpoint may be needed to justify halting, or modifying, the study prematurely. If this criterion were adopted, it would have the practical advantage that the exact number of interim analysis would be of little importance, so no fixed schedule is proposed.

Timing of first main analyses for dissemination:

This will be completed once all patients have completed their final assessment.

Unblinding of randomised treatments:

Any unblinding of randomised treatments will be recorded giving randomised group, centre, date and circumstances of unblinding.

5. Proposed Analyses

5.1 Co-primary endpoint:

The main analysis will be undertaken once all patients have reached 22-24 weeks from randomisation. To assess the efficacy of 12 weeks of amisulpride in Stage 1, the primary outcome of BPRS will be compared using repeated measures regression model. Data from week 4 and week 12 will be the outcome variables and baseline scores will be entered into the model as a covariate. Time will be modelled as a categorical variable. The comparison will be between active amisulpride treatment (arms A and B group together) and placebo (arm C). The six minimisation factors (age, gender, home circumstance, BPRS score, time since onset of symptoms and previous antipsychotic treatment) will also be included as covariates in the repeated measures model. A time by treatment interaction parameter will be included to examine if there is any changing treatment effect over time. Treatment effects are presented with 95% confidence interval and associated p-values in each case. For these analyses a p-value of 0.05 (5% level) will be used to indicate statistical significance. This analysis uses all available visit data which will maximise statistical power to detect any difference at visits

To assess the value of continuing treatment in Stage 2, arm A (amisulpride – amisulpride) will be compared with arm B (amisulpride – placebo). Most patients will have only one outcome time point at week 24 or 36; the protocol has now been amended to shorten Stage 2 to 12 weeks with an additional assessment at about week 16. So, an analysis of covariance will be carried out, using the week 12 BPRS as baseline into the model as a covariate. Confidence intervals for the difference in means will be calculated. Participants who withdraw in Stage 1 will not be included in this analysis.

The BPRS covers the important symptoms elicited in very late-onset schizophrenia-like psychosis patients. In particular the Hostility, Suspiciousness, Hallucinations, Unusual Thought Content, Tension, and Uncooperativeness items of the BPRS all assess important areas of psychopathology in

these patients. The 7-point rating of the BPRS on each of these items generates a sub-score for these six symptoms domains that the protocol pre-specified as those most likely to be affected by the disorder. Scores on the subset range from 6 to 42, with higher scores indicating greater levels of psychopathology. The sub-score will be analysed in the same way the full BPRS analysis, for both Stage 1 and Stage 2.

5.2 Secondary endpoints:

The Simpson-Angus Scale (SAS) is used to see if amisulpride is having an effect on Extrapyramidal side effects (EPSE). The change in SAS scores will be plotted over time to see if there appears to be any increases over time. If the SAS scores remain constant over the assessment time points we can assume that amisulpride is having no effect on Extrapyramidal side effects.

Other continuous measures (EQ-5D and WHOQOL-BREF) will be analysed using the same methods specified in section 5.1, analysis of covariance.

5.3 Sensitivity analyses:

For assessment of change at week 12, analyses will be undertaken carrying forward week 4 assessments for patients with week 4 but not week 12 assessments. To evaluate the effect of compliance on treatment efficacy, the primary analysis will be repeated on a sub-group of participants who adhere to their allocated treatment arm but such analyses are prone to bias so will be interpreted appropriately cautiously.

5.4 Planned subgroup analyses:

Subgroup analyses will be limited to the same variables pre-specified in the protocol as minimisation variable used to balance randomisation:

- Age (60-69, 70-79, 80+)
- Gender
- Home circumstance (Living with spouse/partner, living alone, other)
- BPRS score (30-39, 40-49, 50+)
- Time since onset of symptoms (<6 months, ≥6 months)
- Previous antipsychotic treatment (No, Yes >1 month previously, Yes ≤28 days ago)

These exploratory subgroup analyses will be undertaken, appropriately cautiously, to investigate any influence of the prognostic factors. These subgroups will use standard test for significance of the parameter as an interaction in the repeated measures model.

Any deviations from this plan will be described in the final report.

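### Section 5.2 does not carry out the between-group SAS comparison promised in section 3: it offers a plot and a rule that flat scores mean no drug effect

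*SAP*

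**What the plan says.** In section 3, under Secondary Efficacy Parameters (i), the SAS is rated at five visits, including week 4 and week 16. The contrasts to be compared between groups are given as "The change in SAS between baseline and week 10-12 and between week 10-12 and the final assessment". No model, covariate or test is named there.

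Section 5.2 is where the method should follow. For SAS it says "The change in SAS scores will be plotted over time to see if there appears to be any increases over time", and then gives one rule of inference: "If the SAS scores remain constant over the assessment time points we can assume that amisulpride is having no effect on Extrapyramidal side effects". The next sentence assigns the section 5.1 methods to other continuous measures and lists EQ-5D and WHOQOL-BREF in brackets. SAS is not in the list.

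BPRS starts from parallel wording in section 3: "Change in BPRS score between baseline and the week 10-12 assessment". For BPRS, however, section 5.1 supplies a Stage 1 model: "Data from week 4 and week 12 will be the outcome variables and baseline scores will be entered into the model as a covariate", and "A time by treatment interaction parameter will be included to examine if there is any changing treatment effect over time". It also supplies a Stage 2 analysis of covariance of arm A against arm B with the week 12 score as covariate. The six-item sub-score is covered explicitly: "The sub-score will be analysed in the same way the full BPRS analysis, for both Stage 1 and Stage 2".

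**The concern.** Stage 1 is meant to investigate tolerability as well as efficacy, side-effect risk is secondary objective (i), and SAS is the only side-effect scale this SAP names. Benefit will be reported as an adjusted group difference at each visit with an interval. Harm on SAS, as section 5.2 stands, will be judged by whether a curve looks level.

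That rule can give a wrong conclusion about harm, because it makes no reference to the placebo arm and none to uncertainty. It also leaves the two group comparisons promised in section 3 without a method, and the week 4 ratings without a group estimate.

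**Working it through.** **1. The same kind of outcome, treated differently**

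| Measure | Method in section 5 |
|---|---|
| BPRS | Stage 1 repeated-measures model (weeks 4 and 12, baseline covariate, A+B v C); Stage 2 ANCOVA (A v B) |
| BPRS sub-score | As for BPRS, both stages |
| EQ-5D, WHOQOL-BREF | Section 5.1 methods, ANCOVA |
| SAS | Plot, and a rule that flat scores mean no effect |

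Section 4 promises a repeated-measures analysis for the primary endpoint only, so it does not fill the gap.

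**2. Why the flat-score rule fails**

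Let a be the mean SAS change on amisulpride and c the mean change on placebo. The drug effect is a − c.

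- If a = 0 and c < 0, the amisulpride curve is flat but the effect is −c > 0. The rule says there is none.
- If a = c > 0, scores rise although the effect is zero. The rule gives no way to see this.
- Section 5.2 does not say that the plot is by arm. Pooled over three arms of equal size (assumed), mean change is (2a + c)/3. This is zero whenever c = −2a, when the effect is 3a.
- After week 12, arm B moves to placebo and arm C to amisulpride. A curve over all visits in those arms therefore mixes two treatments.

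**3. What an interval would show**

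The SAP gives no SAS SD and no correlation r between baseline and week 12. Results are therefore in SD units for assumed r, with 90 patients rated at week 12 (section 3, sample size).

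Reproducing the plan's own figure first, for BPRS with SD 9, difference 5 and 60 v 30 patients:

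- SE = 9 × √(1/60 + 1/30) = 9 × 0.2236 = 2.01
- 5/2.01 − 1.96 = 0.52, so power is 70%, as stated
- A 45 v 45 split would give 75%, so 60 v 30 is the split consistent with the plan

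For SAS, with equal SDs at both visits:

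- Raw change: SE = √(2(1 − r)) × 0.2236
- Baseline-adjusted: SE = √(1 − r²) × 0.2236
- Variance ratio, adjusted to raw: (1 − r²)/(2(1 − r)) = (1 + r)/2

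| Assumed r | 95% half-width, raw change | 95% half-width, adjusted | Variance ratio |
|---|---|---|---|
| 0.3 | 0.52 | 0.42 | 0.65 |
| 0.5 | 0.44 | 0.38 | 0.75 |
| 0.7 | 0.34 | 0.31 | 0.85 |
| 0.9 | 0.20 | 0.19 | 0.95 |

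On either analysis, an observed difference of exactly zero leaves differences up to the half-width unexcluded.

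**4. How far the variance ratio depends on equal SDs**

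Let k = baseline SD / week 12 SD. The ratio becomes (1 − r²)/(1 + k² − 2rk). The denominator equals (1 − r²) + (k − r)², so the ratio is 1 when k = r.

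- r = 0.5, k = 0.7: 0.75/0.79 = 0.95, against 0.75 with equal SDs
- r = 0.7, k = 0.8: 0.51/0.52 = 0.98, against 0.85 with equal SDs

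The ratio is nearer 1 than (1 + r)/2 when k lies between 2r − 1 and 1, that is, when the baseline SD is somewhat the smaller. If k > 1, the gain from adjustment is larger than in the table.

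**The case against.** The best defence is that section 3 already commits to a group comparison. In this SAP "change" names an outcome and not an estimator: BPRS has the same wording and is then analysed with baseline as a covariate. A statistician could do the same for SAS without departing from the plan. Choosing week 10-12 as the Stage 1 time point is legitimate, and the lack of a separate week 4 estimate contradicts nothing. Section 4 also promises 95% intervals for efficacy estimates, and SAS is listed under a secondary efficacy heading.

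Much of this stands, and it rules out a stronger reading. A reader might infer that the plan has chosen an unadjusted change analysis and so discards up to a third of its information on harm. The documents do not say that the comparison is unadjusted, and the ratios above also need equal SDs, which the SAP does not give. Nor can the 0.56 SD effect size, set for BPRS, be carried over to SAS to claim a loss of power.

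The defence does not rescue section 5.2. That section addresses SAS directly and states both a method and an inference, so this is not detail left to the protocol. The general promise of intervals needs an estimate to attach to, and section 5.2 specifies none. The word "other" before the listed measures might loosely suggest a shared method, but the bracketed list leaves SAS out.

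**Conclusion.** The point holds as a mismatch between sections 3 and 5.2, together with a rule of inference that is wrong as written. That conclusion rests on the text alone. The half-widths show what a flat or null result would leave open. They assume 60 v 30 patients rated, normal scores, equal SDs and r between 0.3 and 0.9; a strongly skewed SAS would change them.

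The precision gain from baseline adjustment is conditional on raw change being the alternative and on the SD ratio. It may be anything from negligible to about a third of the variance over the cases shown. A reader might also infer that the section 3 comparison is invalid or biased by missing week 10-12 ratings; the SAP gives nothing from which to derive that. This is a free improvement, minor in weight.

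**What to change.** In section 5.2:

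- **Stage 1:** analyse SAS with the section 5.1 repeated-measures model. Use weeks 4 and 12 as outcomes, baseline SAS and the minimisation factors as covariates, categorical time and a time by treatment interaction, with A+B against C. Report the difference at each visit with its 95% confidence interval.
- **Stage 2:** analyse SAS with the section 5.1 ANCOVA, A against B, with week 12 SAS as covariate. Report the difference with its 95% confidence interval.
- **Plot:** keep it, by arm, as description only.
- **Delete** the sentence that infers no effect from constant scores.

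The cost is a few lines of SAP text. The models are already planned for BPRS and the ratings are already scheduled, so no visits or patients are added.

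### Section 5.2 gives the Simpson-Angus Scale only a plot and a flat-line rule, so the between-group comparison promised in section 3 has no model, no estimate and no baseline adjustment

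*SAP*

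**What the plan says.** - **SAP section 3, Secondary Efficacy Parameters, item (i).** The SAS quantity of interest is "The change in SAS between baseline and week 10-12 and between week 10-12 and the final assessment", and this "will be compared between groups to assess EPSE". No model or covariate is named. The scale "will be administered at baseline, then again at week 4, weeks 10-12, week 16 and weeks 22-24 (initially 34-36"), so a baseline and an intermediate visit in each stage are available.
- **SAP section 5.2, on SAS.** "The change in SAS scores will be plotted over time to see if there appears to be any increases over time". If scores stay constant, "we can assume that amisulpride is having no effect on Extrapyramidal side effects". No between-group contrast, estimate or interval is given.
- **SAP section 5.2, next sentence.** "Other continuous measures (EQ-5D and WHOQOL-BREF) will be analysed using the same methods specified in section 5.1, analysis of covariance". Coming straight after SAS, the word *Other* leaves SAS outside these methods.
- **SAP section 5.1, for comparison.** BPRS in Stage 1 is modelled by repeated measures on the two post-baseline visits, adjusted for baseline and the six minimisation factors. Stage 2 is an analysis of covariance with the week 12 score as covariate. The six-item BPRS sub-score is handled in the same way.

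**The concern.** SAS is the one continuous scale in the plan without a baseline-adjusted analysis, and the only side-effect scale that the SAP defines. Side-effects are the first secondary objective, and the background says that benefits have to be balanced against risks.

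Two things are at stake.

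- **The flat-line rule is not an inference about the drug.** Section 5.2 does not say that the plot is by arm, and a plot gives no measure of uncertainty. Constant scores on amisulpride are compatible with harm if placebo scores fall over the same weeks. Rising scores in every arm would not show harm. Only the difference between randomised groups, with its interval, answers the question.
- **If an analyst supplies the missing comparison from section 3 alone, the natural choice is a difference in mean change.** This sets the baseline slope at 1 instead of estimating it. The interval for harm may then be wider than the collected data require, in a trial whose target was cut to at least 100 participants.

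**Working it through.** **1. What the text specifies for each continuous scale**

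| Scale | Between-group contrast | Baseline adjustment |
|---|---|---|
| BPRS and six-item sub-score | Yes (5.1) | Yes (5.1) |
| EQ-5D, WHOQOL-BREF | By reference to 5.1 | By reference to 5.1 |
| SAS | Promised in section 3, absent from 5.2 | None stated |

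**2. Group sizes, checked against the plan's own figure**

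The SAP gives no power for SAS. Its only power figure is 70% for 5 BPRS points, with SD 9, 90 evaluable patients and two-sided 5%. The allocation ratio is not stated. I assume 1:1:1, so A+B against C is 60 against 30.

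- SE = 9 × √(1/60 + 1/30) = 9 × 0.2236 = 2.012
- 5/2.012 = 2.485, and 2.485 − 1.96 = 0.525, which gives power 0.700 (0.691 by the noncentral t)
- A 45/45 split gives 0.750 and does not reproduce the figure

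The 70% is reproduced, which supports 60/30. This figure concerns BPRS and is not affected by the present point.

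**3. Change score against analysis of covariance, equal SDs**

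Let s be the SAS SD at both visits and r the baseline-to-follow-up correlation. The SAP gives neither, so r is an assumed range.

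- Variance of change = 2s²(1 − r)
- Residual variance after adjustment = s²(1 − r²)
- Ratio of change to adjusted = 2/(1 + r), so the SE ratio is √(2/(1 + r))
- 95% half-width in SD units = 1.96 × √variance × 0.2236

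| r | Adjusted ÷ change variance | Change SE wider by | Half-width, change | Half-width, adjusted |
|---|---|---|---|---|
| 0.3 | 0.65 | 24% | 0.519 | 0.418 |
| 0.5 | 0.75 | 15% | 0.438 | 0.380 |
| 0.7 | 0.85 | 8% | 0.339 | 0.313 |
| 0.9 | 0.95 | 3% | 0.196 | 0.191 |

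**4. Unequal SDs**

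Let k be the follow-up SD divided by the baseline SD. The adjusted ÷ change variance ratio is k²(1 − r²)/(k² + 1 − 2rk), and the fitted slope is rk.

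- k = 1.5, r = 0.7: 1.1475/1.15 = 0.998. The slope is 1.05 and there is almost no gain.
- k = 2, r = 0.5: 3/3 = 1.0. The slope is exactly 1 and there is no gain.
- k = 0.7, r = 0.5: 0.3675/0.79 = 0.465. The gain is larger than in the table.

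The ratio does not exceed 1 in any case, in line with the large-sample result, but its size depends on quantities that the SAP does not give.

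**5. What a flat result can exclude**

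At r = 0.5 with equal SDs, an adjusted difference of exactly zero would still have an interval of ±0.380 SD. So even the better analysis could not turn flat scores into proof of no effect.

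**The case against.** The strongest reply is that the SAP never commits to an unadjusted change analysis. A reader might infer that it does, because section 3 speaks of change and section 5.2 leaves SAS out of the adjusted methods. But section 3 also words the BPRS co-primary outcomes as change, and section 5.1 then analyses them with baseline as a covariate. In this document, change can name the outcome without fixing the estimator. That stands: the unadjusted comparison is one possible reading, and the precision loss is conditional on it. What the reply does not do is supply an analysis. For BPRS, section 5.1 replaces the change wording with a model; for SAS nothing does.

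A reader might also infer that a change score over-corrects whenever the correlation is below 1. That needs equal SDs. With a follow-up SD 1.5 times baseline and r = 0.7 it slightly under-corrects and loses almost nothing. Such spread is plausible if the drug raises SAS in only some patients.

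Finally, a reader might expect recent antipsychotic use to unbalance SAS at entry. Previous antipsychotic treatment is a minimisation factor, so that source is largely controlled by design. SAS itself is not a minimisation factor, so some chance imbalance remains possible, but the SAP gives no basis for its size.

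**Conclusion.** The point holds as a defect of specification with a conditional cost in precision. Sections 3 and 5.2 do not agree: one promises a between-group SAS comparison, while the other provides a plot and a rule that cannot support its conclusion. That part rests on the text alone.

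The cost in precision applies only if the gap is filled by an unadjusted comparison of change. With equal SDs the standard error is then about 24% to 3% wider for r from 0.3 to 0.9. With unequal SDs the loss may be larger or close to nil. The direction is secure in large samples; the size cannot be fixed from the SAP. The missing estimate and the no-effect rule matter more than the efficiency loss, and one change to section 5.2 deals with both.

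**What to change.** Rewrite the SAS paragraph of section 5.2 to use the section 5.1 methods:

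- **Stage 1:** A+B against C, repeated measures on SAS at week 4 and weeks 10-12, adjusted for baseline SAS and the minimisation factors.
- **Stage 2:** A against B, analysis of covariance on final SAS, adjusted for SAS at weeks 10-12.
- **Reporting:** the adjusted difference with its 95% confidence interval for each stage. Keep the plot as description only.
- **Delete** the rule that constant scores mean no effect.
- **Section 3:** refer to this model, so that the two sections agree.

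The cost is SAP wording. The SAS visits and the minimisation factors are already collected.

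### Analysis by randomised arm alone cannot support the SAP's reading that constant Simpson-Angus scores mean no extrapyramidal effect; an on-treatment comparison should be reported beside it

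*SAP*

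**What the plan says.** **Attribution rule.** Section 4 (Study population) begins with "Primary analyses of each stage will include all patients who have taken any study treatment in that stage" and then says of that population that "all participants will be analysed in the treatment arm to which they were randomised, whether or not they adhered to the treatment". No separate safety population or on-treatment rule appears anywhere in the SAP.

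**Adherence-based analyses.** Section 4 allows a per-protocol analysis, described as "only those participants who adhere with the treatment allocation) may be carried out but as a sensitivity analysis only"; it names no outcome. Section 5.3 does commit to an analysis of adherers, but as a repeat of the primary analysis, which is BPRS.

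**The extrapyramidal outcome.** Section 3 (Secondary Efficacy Parameters, item i) schedules SAS at baseline, week 4, weeks 10-12, week 16 and the final visit. It says that change to week 10-12, and from there to the final visit, "will be compared between groups to assess EPSE". Section 5.2 specifies only this: "The change in SAS scores will be plotted over time to see if there appears to be any increases over time". It adds that, if scores stay constant, "we can assume that amisulpride is having no effect on Extrapyramidal side effects".

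**Foreseen departures from allocated drug.** The second primary outcome in section 3 is "the proportion of patients withdrawn to open treatment by their physicians because of perceived lack of efficacy". Discontinuation rates are compared under compliance. The SAP does not say which drugs open treatment uses, how often it is expected, or whether SAS is still assessed after withdrawal.

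**The concern.** Side-effect risk is secondary objective (i), and the background section gives the balance of benefit and risk in older patients as the reason for the trial. An SAS score taken at week 10-12 or the final visit may not reflect the allocated drug. A placebo patient already on open treatment may contribute a drug-exposed score to the placebo arm. An amisulpride patient who had signs at week 4 and then stopped may contribute an off-drug score to the amisulpride arm.

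For efficacy, this kind of dilution is usually regarded as conservative. For harm it works against detection. It matters more here because section 5.2 licenses a conclusion of no effect when scores look flat, so a real but diluted effect could be reported as absence of harm. A formal between-arm model for SAS would not remove the problem, because it would still mix exposures within each arm.

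**Working it through.** **1. The plan's own figure.** The SAP states no SAS effect, SD or power. The only figure that can be reproduced is the Stage 1 BPRS power: 5 points, SD 9, 90 assessed, two-sided 0.05. Assuming three equal arms, A+B v C is 60 v 30.

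- Standard error = 9 × √(1/60 + 1/30) = 9 × 0.2236 = 2.012
- 5 / 2.012 = 2.485, and 2.485 − 1.960 = 0.525
- Power = Φ(0.525) = 0.70, which agrees with the stated 70%.

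**2. Model for the SAS difference.** Let D be the on-drug excess in SAS. None of the following quantities is in the SAP:

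- a = fraction of amisulpride patients who have stopped by the visit
- p = fraction of placebo patients on an open antipsychotic at the visit
- s = share of amisulpride stoppers who move to an open antipsychotic
- m = extrapyramidal effect of the open drug relative to amisulpride

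If SAS is still collected after withdrawal:

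observed / D = (1 − a) + a·s·m − p·m

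With s = 0 and m = 1 this becomes 1 − a − p.

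**3. Results.** The power column is illustrative only. It borrows the BPRS standardised effect of 5/9 = 0.56 SD as D and keeps 60 v 30.

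| a | p | s | m | observed / D | power |
|---|---|---|---|---|---|
| 0 | 0 | 0 | 1 | 1.00 | 70% |
| 10% | 10% | 0 | 1 | 0.80 | 51% |
| 20% | 20% | 0 | 1 | 0.60 | 32% |
| 20% | 30% | 0 | 1 | 0.50 | 24% |
| 20% | 20% | 1 | 1 | 0.80 | 51% |
| 10% | 30% | 0 | 0 | 0.90 | 61% |
| 20% | 10% | 1 | 2 | 1.00 | 70% |
| 20% | 10% | 1 | 3 | 1.10 | 78% |

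The first four rows show the dilution mechanism. The last four show its limits. If all stoppers move to an equivalent drug, only p dilutes. If open treatment has no extrapyramidal effect, only stopping dilutes. If stoppers move to a drug with a larger effect, the difference can be unchanged or exaggerated.

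**4. If SAS is not collected after withdrawal.** The formula does not apply. Patients who stop because of extrapyramidal signs then have no later score, and the contrast at week 10-12 or the final visit rests on those who tolerated the drug. That is informative missingness.

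**5. Visit timing.** Section 4 (Late data) accepts late assessments at their nominal visit without limit. A late week 10-12 score in arm C could therefore fall after that arm's scheduled switch to amisulpride, a further possible source of dilution.

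**The case against.** The case against has several sound parts.

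- **Scope.** The rule is written for the primary analyses, and SAS is secondary. This stands: the rule reaches SAS by inference. But the SAP offers nothing else to apply.
- **Per-protocol option.** A reader might infer that the plan strictly bars any exposure-based look at SAS. It does not, because section 4 permits a per-protocol analysis. That analysis is optional, however, and has no outcome or exposure cut-off.
- **The comparison is itself undefined.** Section 3 promises a between-group comparison while section 5.2 gives only a plot. That defect, and the inference drawn from flat scores, are more basic. Repairing the contrast would still leave exposures mixed.
- **Existing safeguards.** Discontinuation and medication taken are compared by allocation, week 4 scores can enter the plot, and patients who withdrew in Stage 1 are left out of the Stage 2 BPRS analysis. Stage 2 was also shortened to keep more patients on treatment at the final visit. These help a reader, but none links an SAS score to the drug being taken.
- **Validity of the randomised comparison.** In a pragmatic trial, comparing arms as randomised answers a proper treatment-policy question. This stands fully. What is missing is a companion analysis.
- **The remedy has its own bias.** On-treatment data lose patients who stop because of extrapyramidal signs, which can also favour no effect. This stands, so the added comparison can only be supportive.

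**Conclusion.** The point holds as a low-cost improvement. Comparing SAS by randomised arm is legitimate, but it does not by itself justify the section 5.2 conclusion that constant scores mean no extrapyramidal effect.

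The size cannot be taken from the SAP. Where SAS is collected after withdrawal, open treatment matches amisulpride in extrapyramidal effect, and stoppers take no antipsychotic, the observed difference is D(1 − a − p), or 0.80 D at 10% and 10%. More generally, dilution needs open treatment to cause such effects and stoppers not to move to a drug with an equal or greater effect; departures from these conditions can reduce, cancel or reverse it.

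A reader might infer that the harm estimate is necessarily pulled towards zero, or that 20% to 50% of the signal is lost. The documents support neither. The direction depends on facts the SAP does not give, and that range only restates assumed values of a + p between 20% and 50%. Smaller fractions would give a smaller loss.

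**What to change.** In section 5.2:

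1. Keep the SAS comparison by randomised arm and state it explicitly: A+B v C in Stage 1, A v B in Stage 2.
2. Report beside it an on-treatment comparison for each stage, using every SAS score, including weeks 4 and 16, taken on allocated medication and before any open antipsychotic.
3. Tabulate by arm the scores taken after a move to open treatment, the last SAS at or before discontinuation, and discontinuations due to extrapyramidal effects where the reason is recorded.
4. State whether SAS is collected after withdrawal. If it is not, treat the gap as potentially informative missing data.
5. Replace the sentence that infers no effect from constant scores with a rule that no such conclusion rests on either comparison alone.

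**Cost.** SAP wording, one additional analysis and some tables, using SAS visits and withdrawal records already planned. The downside is that the on-treatment comparison is not protected by randomisation and loses patients who stop because of extrapyramidal effects, so it should be labelled supportive and should not replace the randomised result.
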